6.9 Packaging and Labeling

All packaging and labeling will be in accordance with applicable regulatory requirements.

6.9.1 Investigational Product

Idursulfase-IT drug product is a sterile liquid formulation for IT administration that is packaged in 2-mL type-I borosilicate glass vials. The drug product is filled to deliver a minimum dose volume of 1 mL per vial with minimal waste and for handling convenience in the clinical setting.

6.9.2 Intrathecal Drug Delivery Device

The SOPH-A-PORT Mini S Access Port is available in one size, individually packaged, with other SOPH-A-PORT Mini S components in double peel-off, sterile, pyrogen-free packaging, sterilized with ethylene oxide. Instructions for use are also included in the packaging. A guidewire is provided in separate double pouch, sterile, pyrogen-free packaging.

Labels are provided on the outer carton and on both the SOPH-A-PORT Mini S box and guidewire/cannula package inside.

6.10 Storage and Accountability

6.10.1 Investigational Product

Idursulfase-IT will be shipped by Shire or a qualified distributor to the clinical study site(s) at 2 to 8 °C (36 to 46 °F). The investigational product should be handled as follows:

- idursulfase-IT vials should be stored at 2 to 8°C (36 to 46°F).
- idursulfase-IT is intended for IT use only.
- It is recommended that idursulfase-IT be filtered prior to use through a standard 0.22 µm filter.
- Perform a visual inspection of each vial. Idursulfase-IT is a clear to slightly opalescent, colorless solution. Do not use if the solution in the vials is discolored or particulate matter is present.
- DO NOT SHAKE. Idursulfase-IT should not be agitated vigorously at any time.
- Withdraw the volume of idursulfase-IT from the vial.
- Do not mix with, or administer in conjunction with other drug solutions.
- Because it does not contain preservatives, idursulfase-IT should be used as soon as possible after it is prepared.
- Idursulfase-IT is supplied in single-use vials. Only 1 dose of idursulfase-IT is to be withdrawn from a vial.

See the Pharmacy Manual for additional details.

The disposition of all investigational product delivered to a Principal Investigator must be recorded on a patient-by-patient basis by completing the Accountability Log. The date and time

of administration of the investigational product and use of the device must be documented on the patient's appropriate CRF.

The Principal Investigator, Clinical Research Coordinator, or designee (eg, Pharmacist) must ensure that all documentation regarding investigational product receipt, storage, dispensing, loss/damaged and return of used/unused product is complete, accurate, and ready for review at each monitoring visit and/or audit. The sites must ensure that the investigational product is available for the monitor to inventory and prepare for return shipment to the Sponsor or designee, if required.

6.10.2 Intrathecal Drug Delivery Device

The disposition of all SOPH-A-PORT Mini S devices delivered to a Principal Investigator must be recorded on a patient-by-patient basis by completing the Accountability Log. The date and time of administration of the investigational product and use of the SOPH-A-PORT Mini S device must be documented on the patient's appropriate CRF.

The Principal Investigator, Clinical Research Coordinator, or designee (eg, Pharmacist) must ensure that all documentation regarding receipt, storage, dispensing, loss/damaged SOPH-A-PORT Mini S devices and return of used/unused SOPH-A-PORT Mini S device(s) is complete, accurate, and ready for review at each monitoring visit and/or audit. The sites must ensure that the SOPH-A-PORT Mini S devices are available for the monitor to inventory and prepare for return shipment to the Sponsor or designee, if required.

The SOPH-A-PORT Mini S and its components are sterile, single-use devices.

Please refer to the IDDD Manual for device return instructions.

6.10.3 Comparator Product

Not applicable to this study.

7 STUDY PROCEDURES

The pivotal study will consist of a Screening period of up to 28 days (during which re-testing of patients who were initially unwilling or unable to comply with all scheduled screening assessments is permitted) prior to randomization (Day 0).

It is planned that patients randomized to the IT treatment arm will undergo surgical implantation of the SOPH-A-PORT Mini S IDDD followed by a post-operative recovery period of at least 14 days prior to the first IT administration of idursulfase-IT. Treated patients will then receive 12 monthly IT injections of idursulfase-IT corresponding to a treatment and assessment interval of 13 (28-day) months from randomization to the EOS evaluations. Likewise, patients randomized to the no IT treatment arm will be assessed over 13 (28-day) months after randomization.

Patients in the IT treatment arm of the pivotal study will be assessed according to the following schedule:

- Screening (Weeks -4 to -1 [Day -28 to Day -1])
- Randomization (Week 0 [Day 0])
- Pre-surgery, Surgery, Follow-up, and Post-operative Recovery (Week 2 [+7 days])
- Treatment and Assessments (Week 4 through Week 48 [± 7 days])
- End of Study (EOS, Week 52 [± 7 days])
- Follow-up (telephone contact) 7 (± 2) days from the Week 52 (or EOS)

Patients in the no IT treatment arm of the pivotal study will be assessed according to the following schedule:

- Screening (Weeks -4 to -1 [Day -28 to Day -1])
- Randomization (Week 0 [Day 0])
- Telephone Contact (Week 2 [+7 days])
- Assessments (Week 4 through Week 48 [± 7 days])
- End of Study (EOS, Week 52 [± 7 days])
- Follow-up (telephone contact) 7 (± 2) days from the Week 52 (or EOS)

The separate substudy is open label and single arm. Patients who meet all entry criteria for participation in the substudy will be considered enrolled on Day 0. Thereafter, it is planned that patients in the separate substudy will undergo surgical implantation of the SOPH-A-PORT Mini S IDDD for the purpose of IT administration of idursulfase-IT and will follow a similar schedule of treatment and assessments as idursulfase-IT-treated patients in the pivotal study.

Patients in the substudy will be assessed according to the following schedule:

- Screening (Weeks -4 to -1 [Day -28 to Day -1])
- Enrollment (Week 0 [Day 0])
- Pre-surgery, Surgery, Follow-up, and Post-operative Recovery (Week 2 [+7 days])
- Treatments and Assessments (Week 4 through Week 48 [± 7 days])
- End of Study (EOS, Week 52 [± 7 days])
- Follow-up (telephone contact) 7 (± 2) days from the Week 52 (or EOS)

Patients will complete EOS assessments at Week 52 (Visit Month 13) and will participate in a follow-up contact (by telephone) approximately 7 days after the EOS visit. (Note that for those patients who enroll in extension study SHP-609-302 within the 7 ± 2 day window of the EOS visit the follow-up contact is not required. If, however, a patient is not enrolled in the SHP-609-302 study within the 7 ± 2 day window of the EOS visit, then the follow-up contact should be completed.)

A patient who discontinues or is withdrawn prior to study completion will be asked to participate in an EOS visit within approximately 30 days after withdrawal or discontinuation (EOS assessments for such patients will be the same as Week 52 assessments), and also to complete a follow-up contact approximately 7 days after the patient's EOS visit. There is no replacement of patients who do not complete the study.

All patients will receive weekly IV Elaprase infusions as prescribed throughout the study.

For treated patients in the pivotal study and patients in the substudy, on IT Dosing Weeks the IV infusion of Elaprase should be scheduled to occur a minimum of 48 hours after IT administration of idursulfase-IT.

See Section 13 for the Schedules of Events for the pivotal study ([Appendix 1](#) and [Appendix 2](#)) and separate substudy ([Appendix 3](#)).

All data collected are to be recorded on the appropriate CRF.

Details for study procedures including sample collection are described in the Study Operations Manual.

7.1 Informed Consent

Prior to conducting any study-related procedures, written informed consent (signed and dated) must be obtained from the patient's parent(s) or legally authorized guardian(s) (and assent from the patient, if applicable). The nature, scope, and possible consequences, including risks and benefits, of the study will be explained by the Investigator or designee in accordance with the guidelines described in Section 11.4. Documentation and filing of informed consent documents should be completed according to Section 11.4.

7.2 Study Entrance Criteria

Each patient will be reviewed for eligibility against the study entrance criteria. Patients who do not meet the study entrance criteria will not be allowed to participate in the study. The reason(s)

for the patient's ineligibility for the study will be documented. No protocol exemptions will be permitted.

7.3 Medical History

A standard medical history of each patient will be obtained at Screening and will include age at onset of Hunter syndrome symptoms, age of Hunter syndrome diagnosis, evidence of iduronate-2-sulfatase deficiency, genotype, family history of Hunter syndrome, Hunter syndrome signs and symptoms in the following domains: head/neck, eyes, mouth, ear, nose, throat, chest/lung, cardiovascular system, abdomen, gastrointestinal system, genitourinary system, skin, skeletal system, neurological system, psychiatric disorders and surgical history.

Patients who do not have a documented diagnosis of Hunter syndrome in their medical history will provide a blood sample at Screening to assay for iduronate-2-sulfatase enzyme activity in plasma, fibroblasts, or leukocytes (patients must exhibit $\leq 10\%$ of the reference laboratory's lower limit of the normal range to confirm diagnosis). These samples will also be assayed for normal enzyme activity level of one other sulfatase in plasma, fibroblasts, or leukocytes (based on the reference laboratory's normal range).

7.3.1 Genotype

Patients who have not had a previous iduronate-2-sulfatase gene (IDS) genotype analysis performed at Greenwood Genetic Center's Diagnostic Laboratory (Greenwood, South Carolina, USA), referred to here as "Greenwood Labs," will provide a blood sample for genotyping to document the diagnosis of Hunter syndrome. Even patients for whom prior genotyping was performed at Greenwood Labs may need to have a repeat analysis performed, if the original information was insufficient for an unambiguous classification of genotype (eg, to document the integrity of the FMR1 and FMR2 genes in patients with large deletion/rearrangement mutations).

Specific instructions concerning genotyping and the timing of enrollment are provided below:

- A Greenwood Labs IDS genotype will be obtained for all patients in the study. If the patient has no Greenwood Labs IDS genotype in his file at the time of informed consent, a blood sample will be drawn at Screening. If the patient has a prior Greenwood Labs genotype in his file, and it indicates the presence of a mutation(s) that is within the IDS locus (eg, small deletion or point mutation), the test will not have to be redone. If the patient has a prior Greenwood Labs genotype in his file, and it indicates the presence of a large deletion/rearrangement mutation but does not confirm the integrity of the FMR1 and FMR2 genes, a new sample may have to be drawn.
- If the patient has no documented IDS genotype at Screening, then enrollment/randomization will have to await the arrival of the Greenwood Labs genotype results.
- If the patient has a locally determined IDS genotype indicating the presence of a small deletion or point mutation, the site may proceed and enroll/randomize him while awaiting the confirmatory results from Greenwood Labs.
- If the patient has a locally determined IDS genotype indicating the presence of a large deletion/rearrangement mutation, then enrollment/randomization will have to await the results of the Greenwood Labs genotype analysis to confirm the integrity of the FMR1 and FMR2 genes.
- If the patient has a Greenwood Labs IDS genotype indicating the presence of a small deletion or point mutation, he can be enrolled/randomized at once.
- If the patient has a Greenwood Labs IDS genotype indicating the presence of a large deletion/rearrangement mutation, he may only be enrolled/randomized if and when a Greenwood Labs genotype confirming the integrity of the FMR1 and FMR2 genes is available, either in his original genotype documentation, or by analysis of a new sample.

7.4 Echocardiogram

An echocardiogram will be performed as part of the study screening assessments. This procedure will not be necessary if the patient has had an echocardiogram performed within 3 months of study entry, the data are available, and deemed satisfactory for evaluation of anesthesia risk.

7.5 Device Related Procedures

7.5.1 IDDD Implantation and Revision

The IDDD will be surgically implanted or revised at the clinical site. Procedures for implantation and revision are detailed in the device's IFU. Standard hospital procedures for surgery will be followed; the patient will be under general anesthesia for this procedure.

The IFU states the device is contraindicated if the patient's body size is too small to support the size of the SOPH-A-PORT Mini S access port (See Exclusion Criterion 13b). An advisory board consisting of neurosurgeons and medical geneticists convened in October 2014, reached a consensus, and determined the device could be implanted in patients >6 months of age. The corresponding minimum weight and length for a 6-month old boy would be 7.1 kg and 65.4 cm, respectively (15th percentile) according to the World Health Organization (WHO) Child Growth Standards; Weight-for-age Boys: Birth to 5 Years and Length-for-age Boys: Birth to 2 Years.²¹

An additional medical device, the catheter passer, is necessary for the implantation procedure. The catheter passer is a sterile, single use device that will be used in the subcutaneous placement of the catheter. The Phoenix Neuro Disposable Catheter Passer, manufactured by Sophysa is CE marked in the EU and cleared under K853370 in the US and may be provided; however, use of other catheter passers compatible with the SOPH-A-PORT Mini S is allowed.

Details of the implantation/revision and malfunctions/failure will be documented on the patient's CRF.

7.5.2 X-ray Verification of Intrathecal Drug Delivery Device Placement

A postoperative X-ray check of the IDDD will be performed following surgery to verify proper installation and confirmation of IDDD placement at the mid-thoracic level. The X-rays may be performed to check placement of the device, as needed, throughout the study, and will be performed at the end of the study (to verify that the IDDD is in the correct position). At a minimum, the date of the X-ray verifying correct IDDD placement will be documented on the patient's CRF. If the device requires revision or replacement during the study, additional X-rays will be taken to document the proper positioning of the device. If the IDDD malfunctions, an X-ray will be performed to assess the potential cause of malfunction.

7.5.3 CSF Sampling Procedure

Cerebrospinal fluid will be sampled via the device. If this is not possible, and if CSF sampling is necessary, either for adherence to the protocol, or to investigate clinical concerns, a lumbar puncture may be performed to sample CSF, either with or without administration of drug afterwards (See Section 4.1.1).

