7.11.7 Intracranial Pressure Measurement

Intracranial pressure (ICP) measurement (cm of H₂O) will be assessed for all patients. The ICP measurement will be conducted by lumbar puncture and while the patient is under anesthesia.

Patients with a surgically implanted IDDD should undergo X-ray prior to lumbar puncture to verify the position of the catheter.

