7.11.10 Cerebrospinal Fluid Assessments

Cerebrospinal fluid samples will be collected via the IDDD or lumbar puncture and used to analyze standard safety laboratory parameters (chemistries, cell counts), albumin, GAG, and concentration of idursulfase enzyme. The CSF samples will also be analyzed for idursulfase-specific antibodies and antibodies with enzyme neutralizing activity (See Section 7.11.11).

Cerebrospinal fluid will be obtained from patients in the treated arm of the pivotal study and in the substudy at Screening (by lumbar puncture and under general anesthesia), during surgical implantation of the IDDD, prior to each intrathecal injection of investigational product, and at the EOS visit. Should the IDDD become clogged, undergo mechanical complications or otherwise not be accessible, the CSF sample may be obtained by lumbar puncture up to 12 times during the treatment phase of the study.

Patients in the no-treatment arm of the pivotal study will undergo lumbar puncture (under general anesthesia) to obtain CSF samples at the Screening and EOS Visits.

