8.4 End of Study: Month 13 (Week 52[\pm 7 days])

8.4.1 Patients in the IT Treatment Group of the Pivotal Study and All Patients in the Substudy

- Physical and neurological examination
- Height and weight
- Head circumference
- Hearing assessment
- Neurodevelopmental assessments
- Differential Ability Scales, Second Edition (DAS-II)
- Bayley Scales of Infant Development, Third Edition (BSID-III) for patients in the substudy only who are too young (<3 years of age) or unable to complete the DAS-II
- Vineland Adaptive Behavior Scales, Second Edition (VABS-II)
- 12-lead ECG
- Vital signs
- Clinical laboratory tests (hematology, serum chemistry, urinalysis)

- Urine GAG and creatinine
- Anti-idursulfase antibody testing (serum and CSF)
- General anesthesia
- Brain MRI
- ICP measurement (by lumbar puncture)
- CSF sample collection. CSF samples will be used to analyze standard laboratory parameters (chemistries, cell counts), as well as GAG, concentration of idursulfase enzyme, albumin, and presence of idursulfase-specific antibodies.
- X-ray
- Health status assessment (EQ-5D questionnaire)
- Concomitant medications, therapies/interventions, and medical/surgical procedures
- Adverse events

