8.4.2 Patients in the No IT Treatment Group of the Pivotal Study

- Physical and neurological examination
- Height and weight
- Head circumference
- Hearing assessment
- Neurodevelopmental assessments:
- Differential Ability Scales, Second Edition (DAS-II)
- Vineland Adaptive Behavior Scales, Second Edition (VABS-II)
- 12-lead ECG
- Vital signs
- Clinical laboratory tests (hematology, serum chemistry, urinalysis)
- Urine GAG and creatinine
- Anti-idursulfase antibody testing (serum and CSF)
- General anesthesia
- Brain MRI
- ICP Measurement (by lumbar puncture)
- CSF sample collection (by lumbar puncture). CSF samples will be used to analyze standard laboratory parameters (chemistries, cell counts), as well as GAG, concentration of idursulfase enzyme, albumin, and presence of idursulfase-specific antibodies.
- Health status assessment (EQ-5D questionnaire)
- Concomitant medications, therapies/interventions, and medical/surgical procedures
- Adverse events

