6.7.5.3 Pharmacodynamic Outcome

- CSF and Urine GAG

CSF and Urine GAG observed levels, the change from baseline (Screening Visit) and percent change from baseline will be summarized by visit and treatment group. Mean observed values (\pm SE) and mean percent change compared to baseline will be plotted over time. The percent change compared to baseline is defined as the value at the corresponding visit multiplied by 100 and divided by the baseline value. One decimal will be kept for the percent compared to baseline. A van Elteren (vE) test, described in Section [6.7.5.1](#), will be used to compare treatment groups on the change from baseline and percent change to the Visit Week 52. Baseline age group (either <6 years or ≥ 6 years) and baseline GCA score (either ≤ 70 or >70) will be used as stratification factors in the van Elteren test. Analysis of both CSF total GAG and CSF heparan sulfate if available will be performed.

- CSF Albumin Concentration and Albumin Quotients

Albumin levels will be measured in samples of CSF and serum at Screening, Weeks 4, 16, 28, 40 and Visit Week 52. CSF albumin concentrations, CSF/serum albumin quotients ($Q_{\text{Alb}} = \text{CSF albumin/serum albumin}$) observed levels, the change and the percent change from baseline (Screening Visit) will be summarized by visit and treatment group to assess the blood-CSF barrier function ([Andersson et al. 1994](#)).

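### The IT-arm Week 52 CSF route is left open (device by default) while controls have lumbar puncture, so the between-arm CSF GAG comparison may be confounded by sampling route

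*Protocol*

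**What the plan says.** For implanted patients Protocol 7.5.3 sets a default, "Cerebrospinal fluid will be sampled via the device", and permits lumbar puncture when that is not possible. Protocol 4.1.1 and SAP 4.1 also name the device as the means of obtaining CSF. Protocol 7.5.2 requires "confirmation of IDDD placement at the mid-thoracic level".

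Protocol 7.11.10 is looser: "Cerebrospinal fluid samples will be collected via the IDDD or lumbar puncture". For the treated arm it places collection "at Screening (by lumbar puncture and under general anesthesia), during surgical implantation of the IDDD, prior to each intrathecal injection" and at the end-of-study visit, and it attaches a route only to Screening. For controls it specifies lumbar puncture at both Screening and end of study. SAP 5.9 repeats this pattern.

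The two Week 52 lists differ. The control list (8.4.2) reads "CSF sample collection (by lumbar puncture". The IT-arm list (8.4.1) has a CSF collection line with no route, although the same list contains "ICP measurement (by lumbar puncture". Protocol 7.11.7 confirms that procedure for all patients: "The ICP measurement will be conducted by lumbar puncture and while the patient is under anesthesia".

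On analysis, SAP 6.7.5.3 says that a van Elteren test, stratified by age group and GCA class, "will be used to compare treatment groups on the change from baseline and percent change to the Visit Week 52". Protocol 10.6.2 planned a Wilcoxon rank-sum test of the same quantities. CSF albumin and the CSF/serum albumin quotient (SAP 6.7.5.3), and CSF chemistries and cell counts (SAP 6.8.2), are summarized by arm without testing.

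**The concern.** The GAG endpoint is a change from a lumbar baseline. In controls it is lumbar to lumbar. In treated patients sampled under the default it is lumbar to device, and in those sampled by lumbar puncture at Week 52 it is lumbar to lumbar again. If CSF drawn through the catheter differs from lumbar CSF in GAG content, that difference enters the IT arm only. It then adds to, or subtracts from, the drug effect in the one formal between-arm test of the pharmacodynamic endpoint. The same applies to the by-arm albumin, protein and cell-count tables, including the albumin quotient that is meant to describe barrier function. The analysis has no stratum, covariate or sensitivity analysis for route. The CRF items listed in Protocol 7.6 describe the injection, not how the CSF was obtained, so the documents do not show that the Week 52 route could be recovered later.

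**Working it through.** The plan gives no figure for CSF GAG or albumin by sampling site, so there is no stated number to reproduce. The check has three steps.

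**1. Routes side by side**

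| Time point | IT arm | Control arm | Protocol source |
|---|---|---|---|
| Screening CSF | lumbar | lumbar | 7.11.10, 8.1.1 |
| Week 4 CSF, before first dose | device by default; lumbar allowed | none | 7.5.3, 8.3.2.2, 8.3.3.2 |
| Week 52 CSF | no route named; device by default; lumbar allowed | lumbar | 7.5.3, 7.11.10, 8.4.1, 8.4.2, Appendix 1 |
| Week 52 ICP | lumbar puncture | lumbar puncture | 7.11.7, 8.4.1, 8.4.2 |

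The Screening and control Week 52 lists both name lumbar puncture on the CSF line, and the IT-arm Week 52 list does not. In Appendix 1 the Screening CSF entry carries the lumbar-puncture footnote and the end-of-study entry does not. Where the visit list is silent, the general default in 7.5.3 is the natural reading, but 7.11.10 and footnote m of Appendix 1 leave either route open.

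**2. What the contrast estimates**

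Let d be the true drug effect on GAG change, s the device-minus-lumbar difference, and p the share of IT-arm Week 52 samples taken through the device. Then

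expected between-arm contrast = d + p × s.

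With lumbar samples in both arms, p = 0 and the contrast is d. The documents give neither s nor p.

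**3. Effect on the planned test over an assumed range of s**

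Inputs:
- Evaluable patients: 32 × 0.9 = 28.8 and 16 × 0.9 = 14.4, taken as 29 and 14 (sample size and up to 10% missing from Protocol 10.2).
- Four strata from two binary factors. The splits (50% and 20%) are an assumption.
- Standard normal change scores and no drug effect (d = 0), with s in SD units of the change score (an assumption, shown as a range).
- 6,000 runs per setting.

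Statistic: within stratum k, with n patients of whom n1 are treated, T = Σ w × [R1 − n1(n+1)/2] and V = Σ w² × n1(n−n1)(n+1)/12. Here R1 is the treated rank sum and w = 1/(n+1). Reject if |T/√V| > 1.96.

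| Assumed shift s (SD) | Rejection, p = 1 | Rejection, p = 0.5 |
|---|---|---|
| 0 | 4.5% | 5.1% |
| 0.1 | 5.5% | 5.3% |
| 0.25 | 10.3% | 6.6% |
| 0.5 | 27.5% | 9.7% |
| 0.75 | 53.1% | 15.1% |
| 1.0 | 77.2% | 24.2% |

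The Monte Carlo standard error near 5% is √(0.05 × 0.95 / 6000) = 0.3 percentage points. The two columns agree with step 2: s = 0.5 at p = 0.5 gives p × s = 0.25 and 9.7%, against 10.3% for s = 0.25 at p = 1.

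**The case against.** Much of the case on the other side stands.

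- A reader might infer that IT-arm Week 52 CSF is drawn through the catheter as a fixed rule. No section says so: 8.4.1 is silent, either route is permitted, and a lumbar puncture under anesthesia takes place at that visit. Device failures, and US patients first dosed by lumbar puncture (Protocol 8.3.1), make the actual mix unknown. Sampling details are deferred to manuals that are not part of these documents (Protocol 7.12). An unspecified route still leaves p uncontrolled.
- A reader might infer that albumin, protein and cell counts are formally compared. They are summarized only, and SAP 6.8 excludes testing of safety data. Only GAG is tested, within the SAP's exploratory section and outside the three gatekeeping families, and SAP 8.5 treats such p-values as descriptive.
- A reader might infer that the GAG effect is an artefact. The documents report no difference by spinal level in any analyte, so s may be zero. Protocol 1.3 describes the Phase I/II GAG reduction at this dose as pronounced, and a large effect would probably survive a modest shift.
- The Week 4 sample precedes the first dose. GAG and albumin are measured on it, and results are summarized by visit, so a Screening-to-Week 4 shift in device-sampled patients would be visible before any drug. This is a real but partial safeguard: it also contains any effect of surgery, controls have no Week 4 CSF, and the planned test still uses the Screening baseline.

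None of this supports leaving the route open when a lumbar procedure is already scheduled in both arms.

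**Conclusion.** The point holds as a possible confounding by route, not as a demonstrated bias. It rests on three facts in the documents: a lumbar baseline in both arms, a device default after implantation with no Week 52 route named for the IT arm, and a GAG test without any term for route. Its size cannot be derived from the documents. Over the assumed range, the false rejection rate runs from about 5% with no shift to 77% with a 1 SD shift and all IT samples from the port. If half the IT samples come from the port, the upper end is 24%. The direction is unknown, so a shift could mimic or mask a GAG reduction. The primary (GCA) and key secondary (ABC) analyses do not use CSF and are untouched. The single-arm substudy has no between-arm contrast to confound. This is a worthwhile low-cost correction to a pharmacodynamic endpoint and not a threat to the trial's main conclusions.

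**What to change.** **Protocol.** Reconcile 7.5.3, 7.11.10, 8.4.1 and 8.4.2. For the IT arm of the pivotal study, state in 8.4.1 and Appendix 1 that the Week 52 CSF used for between-arm comparisons comes from the lumbar puncture already scheduled for ICP. Because 8.4.1 also covers the substudy, limit the wording to the pivotal arm; Appendix 3 needs no change. Record the route of every CSF sample.

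**SAP 6.7.5.3.**
- Use the lumbar sample for the Week 52 GAG test.
- For patients already past Week 52 (SAP 4.2 puts about 27 there at the second blinded variability assessment), add a sensitivity analysis limited to lumbar samples in both arms.
- Report the IT-arm change from Screening to the Week 4 pre-dose sample, by route, as a check on any shift before drug.

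**Cost.** Wording, one data field and one extra analysis, with no new procedure. The last point of the IT-arm monthly series may come from a different site than the earlier ones. The lumbar-only analysis may be small, and it may select treated patients by device function, so it should be read as supportive.
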